- Change from Baseline in SF-36 Physical Component Summary (PCS) and Mental Component Summary (MCS) components and domain scores over time.
- Proportion of subjects by PGIC category over time.
- Proportion of subjects by PGIS category over time.
- Change from Baseline in FACIT-F score over time.
- Change from Baseline in UC-SQ score over time
- Proportion of subjects with all cause hospitalization through Week 8
- Proportion of subjects with all cause surgery through Week 8

In Substudy 3, additional efficacy variables are as follows and will be evaluated:

- Proportion of subjects who discontinued corticosteroid use, remained corticosteroid free for ≥ 90 days immediately before Week 52 and achieved clinical remission per Adapted Mayo score in subjects taking steroids at Baseline (of induction)
- Proportion of subjects achieving response in IBDQ Bowel Symptom domain at Week 52 (increase of IBDQ bowel symptom domain score ≥ 6)

- Proportion of subjects achieving response in IBDQ fatigue item at Week 52 (increase of IBDQ fatigue item score ≥ 1)
- Proportion of subjects who are taking corticosteroids at Baseline (of induction) and are steroid-free over time.
- Proportion of subjects who are taking corticosteroid at Baseline (of induction) and are steroid free at Week 52
- Proportion of subjects who discontinued corticosteroid use and achieved clinical remission per Adapted Mayo score at Week 52 in subjects taking steroids at Baseline (of induction)
- Proportion of subjects achieving clinical remission per Full Mayo Score (defined as a full Mayo score ≤ 2 with no sub-score > 1) at Week 52
- Proportion of subjects who discontinued corticosteroid use and achieved clinical remission per Partial Mayo Score over time in subjects taking steroids at baseline (of induction)
- Proportion of subjects who discontinued corticosteroid use of ≥ 90 days immediately before Week 52 and achieved clinical remission at Weeks 0 and Week 52 of Substudy 3, in subjects who were taking steroids at Baseline (of induction)
- Proportion of subjects who discontinued corticosteroid use of ≥ 90 days immediately before Week 52 and achieved a SFS ≤ 1 (and not worse than Baseline of induction) and RBS = 1 at Weeks 36 and 44 and clinical remission at Week 52, in subjects who were taking steroids at baseline (of induction)
- Proportion of subjects achieving clinical remission per Partial Mayo score over time.

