8.1.3 Definition of Missing Data Imputation

Missing data will be imputed using one or more of the following methods:

Non-Responder Imputation (NRI): In NRI analyses, subjects who prematurely discontinue the study prior to efficacy assessment at Week 8 of Substudy 1 or Substudy 2 Part 1, Week 16 of Substudy 2 Part 2, and Week 44 or Week 52 of Substudy 3 will be considered non-responders with respect to the efficacy endpoint.

Observed Cases (OC): The OC analysis will not impute values for missing evaluations, and thus a subject who does not have an evaluation on a scheduled visit will be excluded from the OC analysis for that visit.

Depending on the magnitude of missing data due to COVID-19, additional appropriate analysis of missing data may be performed with details included in the SAP. The primary approach for handling missing data in the analysis of binary endpoints will use Non-Responder Imputation while incorporating Multiple Imputation (MI) to handle missing data due to COVID-19 (NRI-C). At each visit, subjects will be characterized as responders or non-responders based on MI imputed values if missing due to COVID-19; otherwise, subjects will be considered as non-responders for missing due to other reasons in the NRI-C approach.

For continuous endpoints, missing data will be handled using Mixed-Effect Model Repeat Measurement (MMRM).

The SFS and RBS at an assessment visit will be calculated as an average of the entries recorded into the subject's diary from the most recent consecutive 3-day period prior to each study visit. If diary entries from the 3 consecutive days prior to the visit are not available, the 3 most recent consecutive days in the last 10 days will be utilized. If data are not available for 3 consecutive days, the average of the entries from the most recent 3 non-consecutive days in the last 10 days will be utilized. If less than 3 days of diary data are available, SFS and RBS will be considered missing. Clinical endpoints of abdominal pain and bowel urgency from subject diaries will be measured at the same time period as the SFS and RBS.

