Appendix H. Mayo Scoring System for Assessment of Ulcerative Colitis Activity

The Mayo Scores range from 0 to 12, with higher scores indicating more severe disease. It consists of 4 subscores. Each sub-score ranges from 0 to 3. The 4 components of the Mayo Score are:

Stool Frequency: 0 = Normal number of stools for this subject 1 = 1 – 2 stools more than normal 2 = 3 – 4 stools more than normal 3 = 5 or more stools more than normal

Rectal Bleeding: 0 = No blood seen 1 = Streaks of blood with stool less than half the time 2 = Obvious blood with stool most of the time 3 = Blood alone passed

Findings on Endoscopy: 0 = Normal or inactive disease 1 = Mild disease (erythema, decreased vascular pattern) 2 = Moderate disease (marked erythema, lack of vascular pattern, any friability, erosions) 3 = Severe disease (spontaneous bleeding, ulceration)

Physician's Global Assessment: 0 = Normal 1 = Mild disease 2 = Moderate disease 3 = Severe disease

Note: In Study M14 -234 Substudy 2 and Substudy 3, evidence of friability during endoscopy in subjects with otherwise "mild" endoscopic activity will confer an endoscopic subscore of 2.

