3.0 Endpoints

The induction baseline (thereafter referred to as Baseline) visit date is the date when the first dose of study drug is received during Induction Studies. The baseline value for a variable is defined as the last non-missing value on or before the date of the first dose of study drug during Induction Studies.

The maintenance baseline visit date is on the same day as the final visit in the Induction Studies (thereafter referred to as Maintenance Baseline). The maintenance baseline value for a variable is defined as the last non-missing value on or before the date of the first dose of study drug during Maintenance Study.

The terminologies and efficacy variables are defined as below:

- Mayo Score
 - **Full Mayo Score:** composite score of UC disease activity based on the stool frequency subscore [SFS] (0 – 3), rectal bleeding subscore [RBS] (0 – 3), physician's global assessment [PGA] subscore (0 – 3) and endoscopic subscore (0 – 3). This score ranges from 0 – 12 points with higher scores representing more severe disease.
 - **Partial Mayo Score:** Full Mayo score minus the endoscopic subscore.
 - **Adapted Mayo Score:** Full Mayo score minus the PGA subscore.
 - **Partial Adapted Mayo Score:** Adapted Mayo score minus the endoscopic subscore.
- Clinical Remission
 - **per Full Mayo Score:** Full Mayo score ≤ 2 with no subscore > 1 .
 - **per Adapted Mayo Score:** Adapted Mayo score ≤ 2 , with SFS ≤ 1 and not greater than baseline, RBS of 0, and endoscopic subscore ≤ 1 .
 - **per Partial Mayo Score:** Partial Mayo score ≤ 2 , with no subscore > 1 .
- Clinical Response
 - **per Full Mayo Score:** decrease in Full Mayo score of ≥ 3 points and $\geq 30\%$ from Baseline, PLUS a decrease in RBS ≥ 1 or an absolute RBS ≤ 1 .
 - **per Adapted Mayo Score:** decrease in Adapted Mayo score ≥ 2 points and $\geq 30\%$ from Baseline, PLUS a decrease in RBS ≥ 1 or an absolute RBS ≤ 1 .
 - **per Partial Mayo Score:** decrease in Partial Mayo score ≥ 2 points and $\geq 30\%$ from Baseline, PLUS a decrease in RBS ≥ 1 or an absolute RBS ≤ 1 .

- **per Partial Adapted Mayo Score:** decrease in Partial Adapted Mayo score ≥ 1 point and $\geq 30\%$ from Baseline, PLUS a decrease in RBS ≥ 1 or an absolute RBS ≤ 1 .
- **Endoscopic Improvement:** Endoscopic subscore of 0 or 1.
- **Endoscopic Remission:** Endoscopic subscore of 0.
- **Histologic Improvement:** decrease from Baseline in Geboes score.
- **Histologic Remission:** Geboes score < 2 .

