3.3 Additional Efficacy Endpoints

The following additional efficacy endpoints will be evaluated:

- The achievement of clinical remission per Partial Mayo score and corticosteroid free over time among subjects taking corticosteroid at Baseline in the Induction Study;
- The achievement of clinical remission per Adapted Mayo score and corticosteroid free at Week 52 among subjects taking corticosteroid at Baseline in the Induction Study;
- The achievement of clinical remission per Adapted Mayo score at both Maintenance Baseline and Week 52, and corticosteroid free for ≥ 90 days

immediately preceding Week 52 among subjects taking corticosteroids at Baseline in the Induction Study;

- The achievement of SFS ≤ 1 (and not worse than Baseline), RBS = 1 at both Week 36 and Week 44, clinical remission per Adapted Mayo score at Week 52 and corticosteroid free for ≥ 90 days immediately preceding Week 52 among subjects taking corticosteroids at Baseline in the Induction Study;
- The achievement of clinical remission per Full Mayo Score at Week 52;
- The achievement of clinical remission per Partial Mayo score over time;
- The achievement of clinical response per Partial Mayo score over time;
- The achievement of clinical remission per Adapted Mayo score over time;
- The achievement of SFS = 0, RBS = 0 and endoscopic subscore = 0 over time;
- The achievement of SFS = 0, RBS = 0 and endoscopic subscore ≤ 1 over time;
- The achievement of SFS ≤ 1 , RBS = 0 at Week 28 and clinical remission per Adapted Mayo score at Week 52;
- The achievement of SFS ≤ 1 , RBS = 0 at both Week 28 and Week 52;
- The achievement of SFS ≤ 1 over time;
- The achievement of RBS = 0 over time;
- Change from Baseline in Adapted Mayo score, Full Mayo score, Partial Adapted Mayo score, Partial Mayo score and Mayo subscores over time;
- Change from Baseline in subject-reported stool frequency (absolute values) over time;
- The achievement of histologic improvement at Week 52;
- The achievement of histologic remission at Week 52;
- The achievement of histologic remission at both Maintenance Baseline and Week 52.
- Change from Baseline in histologic score over time;
- The achievement of corticosteroid free over time among subjects taking corticosteroids at Baseline in the Induction Study;
- Change from Baseline in corticosteroid dose over time among subjects taking corticosteroids at Baseline in the Induction Study;
- Change from Baseline in hs-CRP over time;

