12.0 Overall Type-I Error Control

[figure not shown]
The iterative graphical testing procedure is provided in [Figure 2](#). The overall type I error rate of the primary and ranked secondary endpoints for the two upadacitinib doses will be strongly controlled using such multiple testing procedure.⁸ Specifically, the testing will utilize the sequence of hypothesis testing for the primary endpoint followed by the ranked key secondary endpoints in the order as specified in [Section 3.2](#), and will begin with

testing the primary endpoint using α of 0.025 for each upadacitinib dose compared to placebo. Continued testing will follow a pre-specified weight of α allocation between the single hypothesis within the family, as well as between the families of hypotheses across the doses (denoted as node).

In the graph, the arrows specify the weight of α allocation between nodes. Once a hypothesis is rejected (i.e., deemed the endpoint is significant) at its assigned significance level, its significance level will be allocated to the subsequent node. If more than one arrow originates from a node, the significance level will be split between multiple subsequent nodes following the pre-specified weight. The numbers on the arrows denote the weights. For example, the weight 1 denotes 100% transfer of significance level to the next node, and the weight 1/2 denotes 50% and 50% splitting of significance level between the 2 nodes connected to it.

No multiplicity adjustment will be applied to additional efficacy endpoints listed in Section 3.3. The analysis for additional efficacy endpoints will be performed at the nominal α level of 0.05 (two-sided) for each dose.

Figure 2. Graphical Multiple Testing Procedure for Primary and Ranked Secondary Efficacy Endpoints (ITT_A Population)

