3.0	10 May 2021	
 • Removed incidence rate of UC-related hospitalization and surgeries through Week 52 from secondary endpoints in Section 3.2, and add both as additional efficacy endpoints in Section 3.3 • Updated additional endpoints in Section 3.3: added clinical remission per Partial Mayo score and corticosteroid free over time among subjects taking corticosteroid at Baseline in the Induction Study, changed the evaluation of SFS and RBS from Week 40 and 48 to Week 36 and Week 44 in endpoint achievement of $SFS \leq 1$ (and not worse than Baseline), $RBS = 1$ at both Week 36 and Week 44, clinical remission per Adapted Mayo score at Week 52 and corticosteroid free for ≥ 90 days immediately preceding Week 52 among subjects taking corticosteroids at Baseline in the Induction Study. • Clarified the definition of ITT populations and scopes of analyses in data base lock for each ITT population in Section 4.0. • Clarified the subject disposition and compliance summary in Section 5.0 and Section 6.0, respectively • Specified the derivation of confidence interval for difference in proportions between treatment groups using NRI-C approach in Section 8.3.1 in response to a comment from FDA on December 10, 2020. • Updated the potential intercurrent events in Section 8.2 • Added DAMI as a sensitivity analysis for continuous key secondary endpoints to assess the impact of potential departures from the MAR assumption in Section 8.4 • Clarified the analysis method of multi-level categorical endpoints PGIC and PGIS in Section 8.6. The two endpoints will be reported only descriptively using AO approach. Consequently, the random seeds of NRI-C for PGIC and PGIS has been removed from Table D-1. • Added Baseline aminosalicylate use (yes, no) as a subgroup analysis. • Clarified the baseline for safety analysis in Section 9.1. • Added risk difference and 95% CI for TEAE analysis of SA_A and SA_D populations in Section 9.2. • Clarified the interim analysis in Section 11.0. • Updated the type-I error control approach in Section 12.0

Table 3. SAP Version History Summary (Continued)

Version	Date	Summary

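### One additional Substudy 3 endpoint requires RBS = 1 at Weeks 36 and 44, so a subject with no rectal bleeding at those visits counts as a non-achiever

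*SAP*

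**What the plan says.** The Substudy 3 SAP, Section 3.3, lists a composite endpoint for subjects who were on corticosteroids at induction Baseline. They need an SFS of at most 1 that is no worse than Baseline, "RBS = 1 at both Week 36 and Week 44, clinical remission per Adapted Mayo score at Week 52", and at least 90 days off corticosteroids before Week 52. Protocol 5.3.3.3 gives the same rule: "RBS = 1 at Weeks 36 and 44 and clinical remission at Week 52".

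Four other places bear on it:

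- SAP 3.0 defines remission per Adapted Mayo score as an SFS of at most 1 and "not greater than baseline, RBS of 0, and endoscopic subscore" of at most 1.
- Protocol Appendix H defines the lower end of the RBS scale: "0 = No blood seen 1 = Streaks of blood with stool less than half the time".
- A neighbouring endpoint in SAP 3.3 asks for "RBS = 0 at Week 28 and clinical remission per Adapted Mayo score at Week 52".
- In SAP 13.0, the version 3.0 entry says it "changed the evaluation of SFS and RBS from Week 40 and 48 to Week 36 and Week 44 in endpoint achievement of" this same composite, and then repeats it with RBS = 1. The version 4.0 entry lists no correction.

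Under SAP 8.6, binary additional endpoints are compared with placebo for each dose by the CMH test with NRI-C. SAP 12.0 sets a nominal two-sided 0.05 for each dose and states: "No multiplicity adjustment will be applied to additional efficacy endpoints listed in Section 3.3".

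**The concern.** The endpoint combines symptom control at two visits late in maintenance with corticosteroid-free remission at Week 52. A subject with no bleeding at any of the three visits has the best possible course on RBS, yet the equality sign makes that subject a non-achiever. A zero at just one of Weeks 36 and 44 is enough to fail.

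A programmer following the specification would code it this way. The resulting CMH comparison would count subjects who bled at a particular level at Weeks 36 and 44 and had stopped by Week 52. It would not describe sustained corticosteroid-free remission. Correcting the threshold after unblinding would be a post hoc change of endpoint.

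**Working it through.** The plan states no figure for this endpoint, so there is none to reproduce. The check applies the rule to the values RBS can take.

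**Inputs.** Daily scores run from 0 to 3 (protocol Appendix H). The visit RBS is the mean of three diary days, and protocol 8.1.3 adds: "If less than 3 days of diary data are available, SFS and RBS will be considered missing". The rule is RBS = 1 at both visits (SAP 3.3).

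**Attainable values at one visit.** Let s be the sum of three daily scores, so s runs from 0 to 9 and RBS = s/3. That gives 10 values: 0, 1/3, 2/3, 1, 4/3, 5/3, 2, 7/3, 8/3, 3.

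- Pass (s = 3): 1 value.
- Fail: 10 − 1 = 9 values, of which 3 are below 1 (s = 0, 1, 2) and 6 are above 1 (s = 4 to 9).

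**The rule and two possible corrections, by pair of visits (RBS component only).**

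| Week 36 | Week 44 | RBS = 1 (as written) | RBS = 0 | RBS ≤ 1 |
|---|---|---|---|---|
| 0 | 0 | fail | pass | pass |
| 0 | 1 | fail | fail | pass |
| 1 | 0 | fail | fail | pass |
| 1 | 1 | pass | fail | pass |
| 1/3 | 1/3 | fail | fail | pass |
| 2/3 | 2/3 | fail | fail | pass |
| 2 | 2 | fail | fail | fail |

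The written rule is the only one of the three under which the bleeding-free pair (0, 0) fails.

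**Rounding.** Rounding to one decimal, as in Section 6.0 of the Substudy 1 SAP, changes nothing: 2/3 becomes 0.7 and 4/3 becomes 1.3, so only s = 3 gives 1.0. Rounding to whole numbers would let s = 2, 3 and 4 pass, but an RBS of 0 would still fail.

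**Consistency within the endpoint.** The passing pair (1, 1) must be followed by an RBS of 0 at Week 52, because remission requires it. The literal rule therefore requires the bleeding score to change between Weeks 44 and 52.

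These are counts of possible scores, not of patients. The documents give no RBS distribution at Weeks 36 and 44, so neither the size nor the direction of the effect on the arm rates can be computed.

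**The case against.** The literal reading is hard to dispute: the wording is the same in both documents, the ≤ sign for SFS prints correctly in the same bullet, and nothing says that = 1 means at most 1. The stronger objections concern the remedy and the weight.

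- **The intended threshold is not stated.** RBS = 1 could be a slip for = 0 or for ≤ 1. Full Mayo and Partial Mayo remission, also in the SAP 3.3 list, allow subscores up to 1, so a ceiling of 1 has precedent. This stands in part. However, every RBS threshold otherwise written out in that list is 0. The SFS condition in this bullet also mirrors the SFS part of Adapted Mayo remission, whose RBS part is 0. That favours 0 without proving it.
- **The score count does not separate the rule from its correction.** Under RBS = 0, one value passes and nine fail, just as now, and 1/3 and 2/3 still fail. This is correct. The defect lies in which value passes, not in how many.
- **The purpose is inferred.** Neither document says that the endpoint measures persistence of remission. This is true, but no plausible purpose requires bleeding at two visits and its absence at the third.
- **The protocol carries the same wording**, and the earlier change of visit weeks was made in both documents. This stands, and is a reason to align the protocol too.
- **The endpoint is minor.** It is one of many additional endpoints, in a subset, tested at a nominal level. This stands and limits the weight of the point.

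**Conclusion.** The concern holds. As written in both the SAP and the protocol, the endpoint excludes subjects with no bleeding at Week 36 or Week 44 and admits only those whose RBS is exactly 1 at both visits. That conclusion rests on the plain meaning of the equality sign and the published scale. It needs no assumption about patient distributions, and an RBS of 0 fails under any of the rounding rules considered.

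The impact is narrow: one non-ranked endpoint, in subjects on corticosteroids at induction Baseline, outside type I error control. The primary endpoint, the 12 ranked secondary endpoints, the alpha allocation and the sample size are untouched. It should be corrected, because the planned comparison would be uninterpretable as specified. Confidence is high that the rule is wrong as written, and lower that 0 is the threshold the authors meant.

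**What to change.** Before database lock, replace RBS = 1 with RBS = 0 at Weeks 36 and 44 in SAP 3.3, in line with the Week 52 remission definition and the Week 28 endpoints in the same list. If the authors intended another threshold, such as at most 1, the SAP should say so explicitly, in a form under which bleeding-free subjects qualify. The change should be recorded in SAP 13.0, and protocol 5.3.3.3 aligned at the next amendment.

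The cost is one threshold and one version-history line. SAP 1.0 already provides for documented departures from the protocol's analyses, so the SAP correction need not wait for an amendment. No new data are needed: protocol Appendix E schedules the Partial Mayo score, which contains RBS, at both visits, and SAP Appendix D already assigns RBS its NRI-C random seeds.

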3.4 Safety Endpoints

The following endpoints will be included in the safety analyses:

- Treatment emergent adverse events (TEAEs);
- Serious adverse events (SAEs);
- Adverse events of special interest (AESIs);
- Adverse events (AEs) leading to discontinuation of study drug;
- Vital signs and laboratory tests.

4.0 Analysis Populations

Significant non-compliance was identified at an investigational site (original Investigator [REDACTED]). There were 6 subjects enrolled at this site in the Induction Studies who continued into the Maintenance Study. As a result of this finding, efficacy data for these subjects will be excluded from the statistical analyses for the Maintenance Study. Safety data for these subjects will be included in the safety analyses.

Intent-to-Treat (ITT) Populations

ITT population: All subjects who received at least 1 dose of study drug in the Maintenance Study.

ITT_A population: The subset of ITT population who were the first 450 upadacitinib 45 mg QD 8-week induction responders and who were enrolled under the protocol for 52-week maintenance treatment period in Cohort 1. The ITT_A population is the primary analysis population in Cohort 1 for efficacy endpoints.

ITT_B population: The subset of ITT population in Cohort 3 who were upadacitinib 45 mg QD 16-week induction responders.

ITT_C population: The subset of ITT population who were enrolled under the original protocol, Amendment 1 or 2 for 44-week maintenance treatment period.

ITT_D population: The subset of ITT population who were upadacitinib 45 mg QD 8-week induction responders and who were enrolled under the protocol for 52-week maintenance treatment period in Cohort 1.

ITT_E population: The subset of ITT who were placebo, upadacitinib 7.5 mg QD, 15 mg QD or 30 mg QD 8-week induction responders and who were enrolled under the protocol for 52-week maintenance treatment period.

The above populations were annotated as ITT3, ITT3_A, ITT3_B, ITT3_C, ITT3_D and ITT3_E in the protocol. The number "3" was included in the protocol to indicate the Substudy 3 but removed in this Substudy 3-specific SAP for simplicity.

For ITT populations, subjects will be included in the analysis according to the treatment groups that they are randomized to, as applicable.

Table 1. Definition of ITT Populations

ITT_	Cohort	Induction			Maintenance
		Study	Period	Dose	Protocol Type and Remarks
A	1	M14-234 Substudy 1 M14-234 Substudy 2 /M14-675	8-week	UPA 45 mg	52-week First 450 randomized
		M14-234 Substudy 2 /M14-675	16-week	PBO/UPA 45 mg	
B	3	M14-234 Substudy 2 /M14-675	16-week	UPA 45 mg/UPA 45 mg	52-week
C	1, 2, 4	M14-234 Substudy 1	8-week	PBO, UPA 7.5, 15, 30, 45 mg	44-week
D	1	M14-234 Substudy 1 M14-234 Substudy 2 /M14-675	8-week	UPA 45 mg	52-week
		M14-234 Substudy 1 M14-234 Substudy 2 /M14-675	16-week	PBO/UPA 45 mg	
E	1, 2, 4	M14-234 Substudy 1 M14-234 Substudy 2 /M14-675	8-week	PBO, UPA 7.5, 15, 30 mg	52-week

A database lock and unblinded analysis will be conducted for the purpose of regulatory submission after subjects in the ITT_A population complete the Maintenance Study

(i.e., completed Week 52 or prematurely discontinued prior to Week 52). Efficacy analysis for ITT_B, ITT_C and ITT_E population at this database lock will be conducted among subjects who have completed the protocol defined study period or have the potential to complete the protocol defined study period (i.e., at least 52 weeks/44 weeks for subjects enrolled under the protocol with 52-week/44-week maintenance period) but withdrawn from the study.

Safety Populations

SA population: All subjects who received at least 1 dose of study drug in the Maintenance Study.

SA_A population: The subset of SA population who were the first 450 upadacitinib 45 mg QD 8-week induction responders and who were enrolled under the protocol for 52-week maintenance treatment period in Cohort 1.

SA_B population: The subset of SA population in Cohort 3 who were upadacitinib 45 mg QD 16-week induction responders.

SA_C population: The subset of SA population who were upadacitinib 45 mg QD 8-week induction responders and who were enrolled under the protocol for 44- or 52-week maintenance treatment period in Cohort 1.

SA_D population: The subset of SA population who were placebo, upadacitinib 7.5 mg QD, 15mg QD or 30 mg QD 8-week induction responders and who were enrolled under the protocol for 44- or 52-week maintenance treatment period.

SA_UPA population (all upadacitinib safety analysis set): All subjects who received at least one dose of upadacitinib study drug in the Maintenance Study.

Table 2. Definition of Safety Populations

SA_	Cohort	Induction			Maintenance
		Study	Period	Dose	Protocol Type
A	1	M14-234 Substudy 1 M14-234 Substudy 2 /M14-675	8-week	UPA 45 mg	52-week First 450 randomized
		M14-234 Substudy 2 /M14-675	16-week	PBO/UPA 45 mg	
B	3	M14-234 Substudy 2 /M14-675	16-week	UPA 45 mg/UPA 45 mg	52-week
C	1	M14-234 Substudy 1 M14-234 Substudy 2 /M14-675	8-week	UPA 45 mg	44 or 52-week
		M14-234 Substudy 2 /M14-675	16-week	PBO/UPA 45 mg	
D	1, 2, 4	M14-234 Substudy 1 M14-234 Substudy 2 /M14-675	8-week	PBO, UPA 7.5, 15, 30 mg	44 or 52-Week
UPA	Received at least one dose of UPA				

For the safety populations, subjects are assigned to a treatment group based on the "as treated" treatment group, regardless of the treatment randomized. The "as treated" will be determined by the most frequent dose regimen received in the analysis period.

